7.2. SAFETY

Patients will be evaluable for safety if they received at least one partial or complete infusion of PM01183.

All adverse events (AEs) will be graded according to NCI-CTCAE v4.

The safety profile of patients will be monitored throughout the treatment and up to 30 days after the last treatment infusion (EOT) or until the date of death, whichever occurs first.

Treatment delays, dose reduction requirements, G-CSF and/or transfusions requirements, and reason for treatment discontinuation will be monitored throughout the study.

Any treatment-related AEs will be followed until recovery to grade ≤ 1 or stabilization of symptoms, whenever possible.

8. STATISTICAL METHODS

The statistical analysis will be done by the Sponsors or under the Sponsors' authority.

8.1. ENDPOINTS

8.1.1. Primary Endpoint

The primary evaluation endpoint for this phase II study is the ORR in the population evaluable for efficacy.

The ORR is defined as the percentage of patients with a confirmed response, either CR or PR, according to RECIST v1.1.

8.1.2. Secondary Endpoints

- Duration of response (DR), defined as the time between the date when the response criteria (PR or CR, whichever is first reached) are fulfilled to the first date when PD, recurrence or death is documented.
- Clinical benefit, defined as the percentage of patients with ORR or SD > 3 months, according to RECIST v1.1.
- Progression-free survival (PFS), defined as the period of time from the date of first infusion to the date of PD, death (due to any cause), or last tumor evaluation.
- Overall survival rate at one year (1y-OS), defined as the Kaplan-Meier estimate of the probability of patients to remain alive at one year. Overall survival (OS) will be defined as time from the date of first infusion to the date of death or last contact
- Treatment safety: AEs, SAEs, and laboratory abnormalities will be graded according to the NCI-CTCAE (v4), reasons for treatment discontinuation, dose reduction and/or treatment delays.
- PK descriptive analysis and PK/PD correlation, if applicable.
- PGx expression profile of selected putative markers potentially predictive of response to PM01183, in tissues from tumor samples.

8.2. SAMPLE SIZE

The primary endpoint for this phase II study is to evaluate ORR.

- Cohort A (BRCA+):

At least 53 evaluable patients will be recruited to test the null hypothesis that ORR is 20% or less ($p \leq 0.20$) vs. the alternative hypothesis that 40% or more patients have objective response ($p \geq 0.4$). With these assumptions, if the number of evaluable patients with objective response is ≥ 17 , then this would allow the rejection of the

null hypothesis.

- **Cohort A1 (BRAC+/PARPi):**

At least 20 evaluable patients will be for an exploratory analysis: if the number of patients responding is ≥ 4 (20%), the lower limit of the exact binomial 95% confidence interval will be higher than 5% and lack of activity in this subpopulation will be ruled out.

- **Cohort B (unselected):**

At least 64 evaluable patients will be recruited to test the null hypothesis that ORR is 10% or less ($p \leq 0.10$) vs. the alternative hypothesis that 25% or more patients have objective response ($p \geq 0.25$). With these assumptions, if the number of evaluable patients with objective response is ≥ 12 , then this would allow the rejection of the null hypothesis.

The variance of the standardized tests is based on the null hypothesis. The type I error (alpha) associated with this one-sided test is 0.025 and the type II error (beta) is <0.1 ; hence, statistical power is $> 90\%$.

Futility analyses controlled by the Gamma family boundary will be performed when 20 and 30 patients have been evaluated in cohorts A [Gm(-2)] and B [Gm(-1.5)], respectively. If less than four out of 20 patients in Cohort A, or less than three patients out of 30 in Cohort B achieve an objective response, recruitment to that cohort will be stopped. About 110 evaluable patients are expected to be included finally in the three cohorts: Cohort A (BRCA+), Cohort A1 (BRCA+/PARPi), and Cohort B (unselected).

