2. OVERALL STUDY DESIGN

This is a multicenter, open-label, exploratory, phase II clinical trial evaluating the efficacy and safety of PM01183 administration to patients with previously treated MBC, as follows.

Two cohorts of MBC patients will be prospectively evaluated in the trial according to germline BRCA1/2 status (mutated [cohort A] vs. unselected [cohort B]). A third cohort (A1) will include advanced breast cancer patients with deleterious BRAC1/2 mutation who received prior treatment with poly (ADP-ribose) polymerase (PARP) inhibitors:

- Cohort A (BRCA+ cohort): At least 53 evaluable patients with previously known deleterious BRCA1/2 mutation status at study entry.
- Cohort A1 (BRCA+/PARPi cohort): 20 evaluable patients with known deleterious BRCA1/2 mutation status and prior treatment with PARP inhibitors (PARPi).
- Cohort B (unselected cohort): At least 64 evaluable patients without known deleterious BRCA1/2 mutation status at study entry, i.e., either:
 - Patients known to have no deleterious BRCA1/2 mutations (BRCA-), or
 - Patients whose BRCA 1/2 mutation status is unknown (BRCA-UK); BRCA1/2 germline mutation status will be assessed in PM01183 responding patients in this subgroup.

The primary efficacy endpoint of the study is the **overall response rate (ORR)**, defined as the percentage of patients with a response, either complete (CR) or partial (PR), according to RECIST v1.1 (Section [8.1](#)).

An interim analysis based on the primary endpoint (ORR) is planned after 20 and 30 evaluable patients have been treated in cohorts A and B, respectively (see Section [8.2](#) for details). No interim analysis is planned for cohort A1. If less than four out of 20 patients in Cohort A, or less than three out of 30 patients in Cohort B achieve an objective confirmed response, recruitment to that cohort will be terminated. Otherwise, recruitment will continue until at least 53 and 64 evaluable patients are included in cohort A and cohort B, respectively. Sample size and cohort design will be re-evaluated at this point in order to estimate the 95% confidence interval (CI) with the desired precision. Recruitment to either cohort (e.g., Cohort B) might be halted while interim analysis is being performed, if appropriate.

Patients will receive treatment in the absence of progressive disease (PD) or unacceptable toxicity for as long as it is considered to be in their own benefit (see Section [6.2.1.2](#) for details).

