8.3.1. Efficacy Analyses

For the primary endpoint (ORR) the exact binomial estimator and its 95% CI will be used.

The time-to-event variables (DR, PFS and OS) and their set time estimates (e.g., PFS3, PFS6 and 1y-OS) will be analyzed according to the Kaplan-Meier method.

Exploratory comparison of the efficacy results between the two study cohorts will be performed by means of Fisher analysis and logistic regression (ORR), and of log-rank test/Cox regression (time-to-event variables). Additionally, if clinically appropriate, the two cohorts might be pooled into one, whenever differences between cohorts are considered not relevant. In such case, the point estimates and their 95% CIs will be also reassessed in order to obtain more accurate calculations.

Exploratory subgroup analyses (e.g., triple negative, hormonal receptor status, HER-2 overexpression, etc.) will be also performed depending on the sample sizes of each subgroup, if appropriate.

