### **8.11 Interim and Group Sequential Analysis**

An interim analysis based on the primary endpoint (ORR) is planned after 20 and 30 evaluable patients have been treated in Cohorts A and B, respectively. If less than four out of 20 patients in Cohort A, or less than three out of 30 patients in Cohort B achieve an objective confirmed response (CR or PR according to RECIST v1.1), recruitment to that Cohort will be terminated. Otherwise, recruitment will continue until at least 53 and 64 evaluable patients are included in Cohort A and Cohort B, respectively. Sample size and Cohort design will be re-evaluated at this point in order to estimate the 95% confidence interval (CI) with the desired precision. For further analysis details, see section 5.1 Sample size.

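### Cohort A's success count of 17 is right at 53 patients, but enrolment is open-ended, no count is given for larger n, and nothing says whether the count or the exact 95% CI decides

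*Protocol*

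**What the plan says.** Protocol 8.2 states the Cohort A hypothesis as "At least 53 evaluable patients will be recruited to test the null hypothesis that ORR is 20% or less", against an alternative of 40% or more. Under those assumptions H0 is rejected "if the number of evaluable patients with objective response is ≥ 17". The synopsis and SAP 5.1 give the same pair of figures. On the test behind the count, 8.2 says "The variance of the standardized tests is based on the null hypothesis" and "The type I error (alpha) associated with this one-sided test is 0.025", with power above 90%. A futility look stops the cohort if fewer than 4 of the first 20 respond.

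The number of patients is a minimum. Protocol section 2 says that "recruitment will continue until at least 53 and 64 evaluable patients are included in cohort A and cohort B, respectively", and continues: "Sample size and cohort design will be re-evaluated at this point in order to estimate the 95% confidence interval (CI) with the desired precision". SAP 8.11 repeats this: "Sample size and Cohort design will be re-evaluated at this point in order to estimate the 95% confidence interval (CI) with the desired precision". No place in either document updates the success count.

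For analysis, Protocol 8.3.1 says "For the primary endpoint (ORR) the exact binomial estimator and its 95% CI will be used", and SAP 6.2.1 says the same in substance. Neither section names a test.

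Protocol 7.1 and SAP section 2 add that a Cohort B responder of unknown status who is then found to carry a BRCA1/2 mutation is analysed together with Cohort A.

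**The concern.** A fixed count controls the error rate at one sample size only. With a floor on n and a re-evaluation aimed at CI precision, Cohort A may finish above 53, and the plan does not say what count then applies. A reader who applies 17 literally would be using a test looser than the stated 0.025.

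The plan also carries two criteria with no order between them: a count derived from a normal-approximation test, and an exact interval named for the primary endpoint. A two-sided 95% interval corresponds to a one-sided 0.025 test, so readers will expect the two to agree. If they do not, a report could declare the null rejected beside an interval that contains it.

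**Working it through.** **Inputs.** p0 = 0.20, p1 = 0.40, n at least 53, count 17, one-sided alpha 0.025, null variance, futility stop below 4/20 (all Protocol 8.2); exact binomial 95% CI (Protocol 8.3.1, SAP 6.2.1), taken as Clopper-Pearson.

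**Reproducing the plan's figure.** The critical value is n·p0 + 1.96·√(n·p0·(1−p0)) = 10.6 + 1.96·√8.48 = 16.31, so 17 at n = 53. Then z = (17 − 10.6)/√8.48 = 2.198, while 16/53 gives 1.854. Exact power P(X ≥ 17 | 53, 0.40) = 0.9077, or 0.9010 if the futility stop is followed. The count and the power claim both reproduce.

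**Exact alpha at n = 53.** P(X ≥ 17 | 53, 0.20) = 0.0259, or 0.0252 with the futility stop.

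**Keeping 17, and the count each rule would need, as n grows.** z = (17 − 0.2n)/√(0.16n). Exact alpha = P(X ≥ 17 | n, 0.20), with the futility-stop value in brackets. The last two columns give the smallest count with z ≥ 1.96 and the smallest count whose exact 95% lower limit exceeds 20%, each with its exact alpha.

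| n | z at 17 | Exact alpha keeping 17 | z-test count (alpha) | Exact-CI count (alpha) |
|---|---|---|---|---|
| 53 | 2.198 | 0.0259 (0.0252) | 17 (0.0259) | 18 (0.0122) |
| 54 | 2.109 | 0.0310 (0.0300) | 17 (0.0310) | 18 (0.0149) |
| 55 | 2.023 | 0.0367 (0.0354) | 17 (0.0367) | 18 (0.0182) |
| 56 | 1.938 | 0.0432 (0.0414) | 18 (0.0219) | 18 (0.0219) |
| 57 | 1.854 | 0.0505 (0.0480) | 18 (0.0261) | 19 (0.0126) |
| 58 | 1.773 | 0.0585 (0.0553) | 18 (0.0310) | 19 (0.0153) |
| 59 | 1.692 | 0.0675 (0.0633) | 18 (0.0365) | 19 (0.0185) |
| 60 | 1.614 | 0.0772 (0.0720) | 19 (0.0221) | 19 (0.0221) |

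On the declared z test, 17 holds for n = 53 to 55 and fails from 56. The two rules need the same count only at n = 56 and n = 60 in this range.

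**Count against interval at n = 53.** The exact CI is 0.1992 to 0.4632 at 17/53 and 0.2152 to 0.4827 at 18/53. The two criteria therefore disagree at exactly 17 responders, which has probability 0.0137 at ORR 20% and 0.0573 at 40%.

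**Power of the exact-CI rule at 40%** (futility stop in brackets):

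| n | Count | Power |
|---|---|---|
| 53 | 18 | 85.0% (84.6%) |
| 54 | 18 | 87.3% (86.8%) |
| 55 | 18 | 89.3% (88.7%) |
| 56 | 18 | 91.1% (90.4%) |
| 57 | 19 | 87.8% (87.2%) |
| 58 | 19 | 89.7% (89.1%) |
| 59 | 19 | 91.4% (90.6%) |
| 60 | 19 | 92.8% (92.0%) |

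**Effect of moved Cohort B responders.** Each adds one to both numerator and denominator. The number moved is my assumption. If two join 53 enrolled patients, the exact-CI rule needs 18 of 55, which is 16 of the 53 enrolled, and P(X ≥ 16 | 53, 0.20) = 0.051. If three join, it needs 18 of 56, which is 15 of 53, with probability 0.094. Under the z-test counts the same two values arise with one and two moved (17 of 54 and 17 of 55).

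**Cohort B.** At 12/64, z = (12 − 6.4)/√5.76 = 2.33, exact alpha is 0.0236 (0.0233 with its futility stop), and the exact 95% lower limit is 10.08%, above the 10% null.

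**The case against.** The strongest reply is that the sentence containing 17 follows directly on the figure of 53 and refers back to those assumptions, so the natural reading is 17 of 53. That stands: the denominator is implied, and what is missing is only a rule for any other n.

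It is also fair that the excess at n = 53 is 0.0009 (0.0002 with the futility stop), that the CI conflict there is a single outcome with a lower limit of 19.92% against 20%, and that designing on a normal approximation and reporting an exact interval is common in a trial labelled exploratory. The route above 53 is permitted rather than planned. No larger target is given, the timing of the re-evaluation is ambiguous, and the overall expectation of about 110 is below the sum of the three cohort minimums (53 + 20 + 64 = 137).

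These points reduce the weight of the concern but do not remove it. Protocol 8.2 states a formal null, alpha, power and rejection threshold, and section 1.3 ties the 40% target to further research. The total of about 110 does not cap Cohort A.

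A reader might infer that 17 was miscalculated, or that the trial plans to run at an alpha of 0.043 to 0.05. The documents support neither. The count is right for its test at n = 53, and the higher values arise only if someone keeps 17 at n = 56 or 57, where the declared test already requires 18.

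**Conclusion.** The point holds as a gap in the decision rule for Cohort A's primary endpoint, and it should be closed. The count is correct at n = 53 and usable on the declared z test through n = 55. Beyond that the plan gives no count, and keeping 17 would give exact alpha of 0.043 at 56 and 0.0505 at 57. At 17/53 the count and the planned interval give opposite answers, with no statement of which governs.

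These figures assume independent patients with a common response rate, a Clopper-Pearson interval, and a Cohort A analysis limited to patients enrolled in it. The bracketed values also assume that the futility stop is followed.

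A reader might extend the criticism to Cohort B because its count is paired with a minimum in the same way. At 12/64 the count, the exact alpha and the interval agree. If Cohorts A and A1 reach 53 and 20, about 110 in total leaves about 37 for Cohort B (110 − 53 − 20), so growth past 64 looks unlikely. Its count is sound and needs only to be tied to n = 64.

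**What to change.** Choose one option before results are known, and write it into Protocol 8.2, the synopsis and SAP 5.1.

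(a) **Keep the z test.** State the rule as at least 17 of 53, and give counts for other n: 17 for 53 to 55, 18 for 56 to 59, 19 at 60. State exact alpha as about 0.026 at n = 53 and 0.022 to 0.037 over n = 53 to 60. Say that the count governs and that the exact CI is descriptive. Cost: no loss of power, but alpha is acknowledged to be slightly above 0.025 at most n.

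(b) **Let the exact interval decide.** Reject H0 if the lower limit of the exact two-sided 95% CI exceeds 20% at the number of evaluable patients enrolled in Cohort A: at least 18 for n = 53 to 56, at least 19 for n = 57 to 60. Protocol 8.2 already uses an exact-CI limit for Cohort A1. Restate power at each n from the table above. Cost: power of 85.0% at n = 53. Reaching 56 restores 91.1%, but power falls back to 87.8% at 57 and 89.7% at 58, so a statement that three more patients suffice would mislead unless n is fixed at 56.

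Under either option, say that the test uses only patients enrolled in Cohort A and excludes BRCA-mutated Cohort B responders analysed with it under Protocol 7.1 and SAP section 2. They are all responders and would inflate alpha. They can be shown in a separate supportive estimate. For Cohort B, write the count as 12 of 64.

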8.2.1. Randomization

Not applicable.

8.3. STATISTICAL ANALYSIS

Frequency tables will be prepared by cohort for categorical variables, whereas continuous variables will be described by means of summary tables that will include the median, minimum, and maximum of each variable.

8.3.1. Efficacy Analyses

For the primary endpoint (ORR) the exact binomial estimator and its 95% CI will be used.

The time-to-event variables (DR, PFS and OS) and their set time estimates (e.g., PFS3, PFS6 and 1y-OS) will be analyzed according to the Kaplan-Meier method.

Exploratory comparison of the efficacy results between the two study cohorts will be performed by means of Fisher analysis and logistic regression (ORR), and of log-rank test/Cox regression (time-to-event variables). Additionally, if clinically appropriate, the two cohorts might be pooled into one, whenever differences between cohorts are considered not relevant. In such case, the point estimates and their 95% CIs will be also reassessed in order to obtain more accurate calculations.

Exploratory subgroup analyses (e.g., triple negative, hormonal receptor status, HER-2 overexpression, etc.) will be also performed depending on the sample sizes of each subgroup, if appropriate.

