## 4 PATIENTS EVALUABILITY CRITERIA

The study population will include patients with MBC histologically proven.

Analysis sets definitions:

- “All Included Patients” analysis set is defined as all patients recorded in the database who are included in the trial, independently of whether they have received the study drug or not.
- “All Treated Patients” analysis set is defined as all included patients who have received at least part of one infusion of PM01183.
- “All Evaluable Patients” analysis set is defined as all eligible patients who have at least one complete infusion of PM01183, and either have at least one assessment (as per RECIST v1.1) or have been categorized as “treatment failures”. Patients who discontinue treatment due to any treatment-related toxicity before an appropriate tumor assessment has been performed or those withdrawn after more than two weeks on treatment without any formal evaluation will be defined as “treatment failures”. These patients will be included as inevaluable for response in the analysis of objective response as per RECIST v1.1, although they will not need to be replaced as they will be considered evaluable for efficacy.
- “All Responder Patients” analysis set is defined as all evaluable patients who have had CR or PR as overall best response according to the RECIST v1.1 criteria.

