### 4.2 *Efficacy Populations*

The “All Evaluable Patients” analysis set will be used for the primary endpoint analysis of ORR and for the secondary endpoints of PFS, 1y-OS and clinical benefit rate.

The “All Responder Patients” set will be used for the secondary endpoint analysis of DR.

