### **6.2.2 Secondary Endpoints**

Time-to-event endpoints (DR, PFS and OS) and their set time estimates (i.e. PFS3, PFS6 and 1y-OS) will be analyzed according to the Kaplan-Meier method.

A log-rank test or Cox regression for time-to-event endpoints could be performed as supportive analysis to compare both Cohorts.

If relevant, efficacy parameters versus baseline covariates will be analyzed and appropriate test will be used (i.e., the Fisher exact test and logistic regression for categorical variables, the log-rank test or Cox regression for time-to-event variables, etc.).

If appropriate, exploratory multivariate models (main effects or including interaction terms, if appropriate) will include all prognostic factors/covariates widely reported and recognized by oncologists: Cohort (BRCA (+) vs. BRCA (-) or unknown), BRCA (1 vs. 2 in cohorts A and A1), initial dose (7 mg FD vs 3.5 mg/m^2), age, age at diagnosis, race (Caucasian vs. other), baseline Eastern Cooperative Oncology Group performance status (ECOG PS) (0 vs. >0), histology type (Ductal vs. lobular carcinoma), histology grade (poorly vs. other), stage at diagnosis, primary tumor site (unilateral breast vs. bilateral), hormone receptor positive (estrogen or progesterone receptor +, or both +) vs. triple negative, HER-2 receptor (positive vs. negative), site of current disease such as liver metastases (yes vs. no), CNS metastases (yes vs. no), lung metastases (yes vs. no), non-visceral (including bone, skin, subcutaneous and lymph node vs. other), number of prior metastatic sites (1 vs. >1), body mass index (BMI), height, weight, body surface area (BSA), time from diagnosis to first infusion, prior surgery (yes vs. no), prior radiotherapy (yes vs. no), prior advanced treatment lines, prior advanced chemotherapy lines (0-1 vs. 2-3), prior anthracyclines (yes vs. no), prior taxane (yes vs. no), prior platinum (yes vs. no), prior PARPi (yes vs. no), last prior therapy PFS, first advanced chemotherapy PFS, last advanced chemotherapy PFS, PFS for anthracycline, taxane and platinum therapy, hormonotherapy (yes vs no), adjuvant/neoadjuvant therapy (yes vs no), platinum-free interval (in months), presence of any bulky (< 50 mm vs.  $\geq$  50 mm) lesion, albumin at baseline, CA-15.3 or 27.29 at baseline, any relevant concomitant medication at baseline (to be determinate by the oncologist) (yes vs. no) and the sum of all target lesion diameters.

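### The exploratory cohort comparison extends log-rank/Cox to duration of response, which exists only in responders, so its hazard ratio cannot be read as a BRCA effect on durability (minor; cheap to fix)

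*Protocol*

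**What the plan says.** Protocol 8.3.1 opens its time-to-event paragraph with "The time-to-event variables (DR, PFS and OS) and their set time estimates", to be analysed by Kaplan-Meier. The next paragraph states that "Exploratory comparison of the efficacy results between the two study cohorts will be performed", using Fisher and logistic regression for ORR "and of log-rank test/Cox regression (time-to-event variables". Nothing takes DR out of that class.

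SAP 6.2.2 uses the same list, "Time-to-event endpoints (DR, PFS and OS) and their set time estimates", and adds: "A log-rank test or Cox regression for time-to-event endpoints could be performed as supportive analysis to compare both Cohorts". The protocol therefore commits to the comparison, while the SAP only permits it.

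The population for DR is narrower than for the other two endpoints. SAP 4.2 says the All Responder Patients "set will be used for the secondary endpoint analysis of DR", and SAP 4 says that this "analysis set is defined as all evaluable patients who have had CR or PR as overall best response". Protocol 8.1.2 starts the DR clock at response: it is "defined as the time between the date when the response criteria (PR or CR, whichever is first reached) are fulfilled" up to progression, recurrence or death. PFS and OS run from first infusion in all evaluable patients.

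**The concern.** Response is an outcome of treatment, and the study rationale (Protocol 1.3) hypothesises that BRCA mutation makes tumours more sensitive to the drug. If so, some Cohort A patients respond because of the mutation. They enter Cohort A's DR curve and have no counterpart in Cohort B's, where similar patients are non-responders and are absent. The two responder sets are then different kinds of patients, even if the cohorts were perfectly balanced at baseline.

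A patient who moves from no response to a short response is better off, yet she pushes the DR hazard ratio against Cohort A. A patient who moves to a long response pushes it the other way. The sign therefore depends on who was added to the responder set as well as on whether BRCA status lengthens or shortens responses. A reader given a DR hazard ratio and p-value by cohort would naturally take them as evidence about durability.

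**Working it through.** **The plan's own figures.** Neither document gives a figure for the DR comparison. The sample sizes and rates used below come from Protocol 8.2, which claims power above 90% for the single-arm ORR tests. Exact binomial power is 90.8% for Cohort A (53 patients, at least 17 responses, true rate 40%) and 90.7% for Cohort B (64 patients, at least 12 responses, true rate 25%). Treating the futility looks as binding gives 90.1% and 90.3%. The stated figure reproduces.

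**Responder sets at those rates.**
- Cohort A: 53 × 0.40 = 21.2 responders.
- Cohort B: 64 × 0.25 = 16.0 responders.
- If 25% would respond in either cohort, the extra share in A is 0.40 − 0.25 = 0.15. That is 0.15/0.40 = 37.5% of A's responders, about 53 × 0.15 = 8 patients.

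**Assumptions not in the documents.** The design alternatives are the true rates. DR is exponential. Common responders have a median DR of 6 months in both cohorts. Extra responders in A have median *m*, varied from 2 to 10 months.

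**DR curves.**
- Cohort B: S(t) = 2^(−t/6), median 6.0 months.
- Cohort A: S(t) = 0.625 × 2^(−t/6) + 0.375 × 2^(−t/*m*).

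**Mean time in response over all patients, non-responders counted as 0.** This version has no time limit; an exponential with median *m* has mean *m*/ln 2.
- Cohort B: 0.25 × 6/0.693 = 2.16 months.
- Cohort A: 2.16 + 0.15 × *m*/0.693. For *m* = 3 this is 2.16 + 0.65 = 2.81.

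**Simulation of 53 vs 64 patients, log-rank/Cox among responders only.** Two censoring schemes were used: a fixed cut 12 months after response (median log-rank hazard ratio across trials) and uniform censoring between 6 and 18 months (large-sample Cox hazard ratio, plus 4,000 trials for the percentages). Hazard ratios are A vs B, and values above 1 are against A.

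| Median DR of extra responders, *m* (months) | Median DR in A (months) | HR, 12-month cut | HR, censoring 6–18 months | Trials pointing against A | Significant against A | Significant for A | Mean time in response, A vs B (months) |
|---|---|---|---|---|---|---|---|
| 2 | 3.8 | 1.4 | 1.38 | 81% | 13.8% | 0.2% | 2.60 vs 2.16 |
| 3 | 4.6 | 1.25 | 1.28 | 74% | 9.0% | 0.4% | 2.81 vs 2.16 |
| 4 | 5.1 | 1.14 | 1.15 | 66% | 5.7% | 0.9% | 3.03 vs 2.16 |
| 6 | 6.0 | 1.0 | 0.97 | 50% | 2.8% | 3.0% | 3.46 vs 2.16 |
| 8 | 6.7 | 0.88 | 0.90 | 40% | 1.5% | 4.6% | 3.90 vs 2.16 |
| 10 | 7.2 | 0.82 | 0.83 | 31% | 0.7% | 7.4% | 4.33 vs 2.16 |

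The percentages come from the second scheme, with a nominal 2.5% on each side. At *m* = 6 the true hazard ratio is 1, and 0.97 is simulation error. In every row the common responders have the same DR distribution in both cohorts. BRCA status shortens nobody's response, yet the hazard ratio runs from about 1.4 to about 0.8. The last column favours A throughout because the extra responders can only add time in response.

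**The case against.** The strongest reply is that the plan nearly does the right thing already. The protocol calls the comparison exploratory, and the SAP says only that it could be performed. SAP Table 11.3.2.1 presents DR as counts, a median and estimates at 6 and 12 months, with no test. The regression tables in SAP 11.3.3 cover response rate, PFS and OS, and DR is absent. No sample size, futility rule or success criterion uses a DR comparison. All of this stands and sets the weight of the point.

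A reader might infer that the analysis will make the BRCA+ cohort look less durable. The documents do not support that. They give no durations and do not suggest that mutation-driven responses are shorter; equal durations give no distortion and longer ones reverse it. A reader might also infer that the DR test bears on the secondary objective of whether BRCA mutation predicts response. That objective concerns response itself, which 8.3.1 assigns to Fisher and logistic regression on ORR. Nor does the design predict a 40% vs 25% contrast: these are alternatives for two separate single-arm tests, used here only as a working assumption.

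It is also fair to say that a responder-only hazard ratio correctly describes the responders observed, and that PFS and OS comparisons between non-randomised cohorts are open to confounding too. Both are true. But conditioning on response is an additional problem that PFS and OS do not share, and baseline adjustment does not in general remove it.

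What remains is that the protocol says the comparison will be done on a class that includes DR, and neither document excludes or qualifies it.

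**Conclusion.** The point holds as a minor one. As worded, Protocol 8.3.1 commits to, and SAP 6.2.2 permits, a between-cohort log-rank/Cox comparison of DR in a set selected on an outcome BRCA status is hypothesised to affect. Its hazard ratio has no valid reading as a BRCA effect on durability, in either direction.

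Under the stated assumptions the hazard ratio is about 1.4 to 0.82 as the extra responders' median DR goes from 2 to 10 months. With about 37 responders in all (21.2 + 16.0), the practical result is a misleading estimate and direction more often than a significant p-value: 13.8% significant against A at the 2-month extreme, 9.0% at 3 months. These sizes rest on assumed true ORRs, an assumed 6-month common median and exponential durations; none is in the documents except the ORR alternatives. The finding that the sign depends on the added responders does not rest on those particular values.

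**What to change.** In Protocol 8.3.1 and SAP 6.2.2, state that between-cohort log-rank/Cox comparisons apply to PFS and OS only. Report DR by cohort descriptively: Kaplan-Meier median with 95% CI and the set-time estimates, without a hazard ratio or p-value. This matches what SAP Table 11.3.2.1 already lists, apart from adding the confidence interval. The SAP sentence on testing efficacy parameters against baseline covariates needs the same limit, because cohort is the first covariate listed there.

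Optionally, add mean time in response within 12 months of first infusion over all evaluable patients, counting non-responders as 0. It needs a censoring-adjusted estimator, because DR is censored at subsequent therapy and the clinical cut-off may leave some patients with less than 12 months. It should be described as combining response rate and duration. It would still be affected by the rule that moves unknown-status Cohort B responders found to be mutated into Cohort A, so that rule should be noted beside the result.

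The cost is one sentence in each document and the loss of one exploratory p-value. No new data are needed.
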